3.2.2 Nivolumab Mechanism of Action

Cancer immunotherapy rests on the premise that tumors can be recognized as foreign rather than as self and can be effectively attacked by an activated immune system. An effective immune response in this setting is thought to rely on immune surveillance of tumor antigens expressed on cancer cells that ultimately results in an adaptive immune response and cancer cell death. Meanwhile, tumor progression may depend upon acquisition of traits that allow cancer cells to evade immunosurveillance and escape effective innate and adaptive immune responses.^{14,15,16} Current immunotherapy efforts attempt to break the apparent tolerance of the immune system to tumor cells and antigens by either introducing cancer antigens by therapeutic vaccination or by modulating regulatory checkpoints of the immune system. T-cell stimulation is a complex process involving the integration of numerous positive as well as negative co-stimulatory signals in addition to antigen recognition by the TCR.¹⁷ Collectively, these signals govern the balance between T-cell activation and tolerance.

PD-1 is a member of the CD28 family of T-cell co-stimulatory receptors that also includes CD28, CTLA-4, ICOS, and BTLA.¹⁸ PD-1 signaling has been shown to inhibit CD-28-mediated upregulation of IL-2, IL-10, IL-13, IFN- γ and Bcl-xL. PD-1 expression also been noted to inhibit T cell activation, and expansion of previously activated cells. Evidence for a negative regulatory role of PD-1 comes from studies of PD-1 deficient mice, which develop a variety of autoimmune phenotypes.¹⁹ These results suggest that PD-1 blockade has the potential to activate anti-self T-cell responses, but these responses are variable and dependent upon various host genetic factors. Thus, PD-1 deficiency or inhibition is not accompanied by a universal loss of tolerance to self-antigens.

In vitro, nivolumab (BMS-936558) binds to PD-1 with high affinity (EC₅₀ 0.39-2.62 nM), and inhibits the binding of PD-1 to its ligands PD-L1 and PD-L2 (IC₅₀ \pm 1 nM). Nivolumab binds specifically to PD-1 and not to related members of the CD28 family such as CD28, ICOS, CTLA-4 and BTLA. Blockade of the PD-1 pathway by nivolumab results in a reproducible enhancement of both proliferation and IFN- γ release in the MLR. Using a cytomegalovirus (CMV) re-stimulation assay with human PBMC, the effect of nivolumab on antigen specific recall response indicates that nivolumab augmented IFN- γ secretion from CMV specific memory T cells in a dose-dependent manner versus isotype-matched control. In vivo blockade of PD-1 by a murine analog of nivolumab enhances the anti-tumor immune response and result in tumor rejection in several immunocompetent mouse tumor models (MC38, SA1/N, and PAN02).²⁰

3.2.3 Bempegaldesleukin Mechanism of Action

Bempegaldesleukin (NKTR-214) is a prodrug of a conjugated cancer immunotherapy cytokine that exerts its biological activity by binding to the interleukin-2 (IL-2) receptor and subsequent activation of effector T cells. As a PEGylated human recombinant IL-2 molecule of aldesleukin with an average of 6 releasable polyethylene glycol (PEG) chains, bempegaldesleukin can be administered conveniently in the outpatient setting using an antibody-like dosing regimen. The polymer conjugation renders the cytokine initially inactive. Upon intravenous (IV) administration, the PEG chains slowly release to generate the active cytokine species (mainly 2-PEG-IL-2 and 1-

PEG-IL-2) that have a peak plasma concentration of 24 to 48 hours after infusion. The slow generation of the 2-PEG-IL-2 and 1-PEG-IL-2 significantly mitigates the rapid-onset, systemic cytokine-related toxicities associated with high dose IL-2.

The polymer conjugation of bempegaldesleukin promotes biased signaling through the IL-2 receptor beta gamma (IL-2R $\beta\gamma$). Specifically, the location of the bempegaldesleukin PEG chains interferes with the binding to the IL-2 alpha receptor subunit responsible for the undesirable effect of activating regulatory T cells (Tregs) in the tumor while continuing to permit binding to the IL-2R $\beta\gamma$ (CD122) receptor. Upon infusion, bempegaldesleukin preferentially increases the proliferation, activation, and effector function of tumor antigen-specific CD8⁺ T cells and natural killer (NK) cells within the tumor microenvironment (TME) over expansion of unwanted intra-tumoral Tregs that are activated through the IL-2 receptor alpha beta gamma (IL-2R $\alpha\beta\gamma$).^{21,22,23,24,25} Consistent with this mechanism of action, recent nonclinical studies demonstrate strong synergy of bempegaldesleukin with adoptive T cell therapy (ACT), with PD-1 checkpoint blockade, and with tumor antigen-specific vaccination, in a variety of mouse models.^{24,25} This synergy was mediated by expansion of tumor-specific CD8⁺ T cells in the periphery and tumor, without strong expansion of Tregs in the tumor tissue.

[figure not shown]
Bempegaldesleukin also correspondingly promotes expression of PD-1 on the surface of CD8⁺ T cells and induction of a Type II interferon gene signature in the TME, driving cell surface expression of programmed cell death ligand 1 (PD-L1) on tumor cells.²⁶

[figure not shown]
The immunological properties of bempegaldesleukin with the induction of tumor-infiltrating lymphocytes and upregulation of the PD-1/PD-L1 axis makes bempegaldesleukin a potentially promising combination therapy for use with checkpoint inhibitors that target and inhibit the PD-1/PD-L1 pathway. Moreover, the safety profile of bempegaldesleukin generally does not overlap with that of checkpoint inhibitors, further supporting the use of bempegaldesleukin as a potentially complimentary combination partner with checkpoint inhibitors.

[figure not shown]
3.2.4 Clinical Experience with Nivolumab

[figure not shown]
Nivolumab has demonstrated safety and efficacy as monotherapy in the treatment of advanced melanoma in treatment naive patients in two Phase 3 trials. In CheckMate-066 previously untreated melanoma patients with advanced melanoma without BRAF mutations were randomized treatment with either nivolumab versus dacarbazine. There was a 58% reduction in the risk of death with nivolumab treatment group (hazard ratio [HR] for death, 0.42 [99.79% CI, 0.25–0.73] $P < 0.001$).²⁷ CheckMate-067 was a double-blind, Phase 3 study to evaluate the efficacy and safety of nivolumab monotherapy and nivolumab plus ipilimumab combination therapy compared to ipilimumab monotherapy in metastatic or unresectable melanoma regardless of BRAF mutation status. Nine hundred forty-five participants were randomized 1:1:1 to receive either 3 mg/kg of nivolumab every 2 weeks (plus ipilimumab-matched placebo); 1 mg/kg of nivolumab every 3 weeks plus 3 mg/kg of ipilimumab every 3 weeks for 4 doses, followed by 3 mg/kg of nivolumab every 2 weeks; or 3 mg/kg of ipilimumab every 3 weeks for 4 doses (plus nivolumab-matched placebo). The overall response rate was 44% in the nivolumab monotherapy arm and 19% in the ipilimumab monotherapy arm. The hazard ratio for progression or death was 0.55 (95% CI, 0.45

to 0.66) with nivolumab versus ipilimumab. The rate of OS at 3 years was 52% in the nivolumab group, as compared with 34% in the ipilimumab group.¹³ The median duration of response was not reached in the nivolumab monotherapy group and was 19.3 months in the ipilimumab group. These data led to FDA and EMA approval of nivolumab monotherapy as frontline treatment in patients regardless of BRAF mutation status.

3.3 Benefit/Risk Assessment

3.3.1 Bempegaldesleukin Safety Profile

Bempegaldesleukin was designed to mitigate the severe toxicities associated with rapid systemic immune activation seen with administration of aldesleukin. The identified risks of bempegaldesleukin include hypotension, IL-2 mediated AEs (eg, flu-like symptoms, rash, pruritus, fatigue, hepatic transaminase elevations, and serum creatinine elevations), infusion-related reactions/hypersensitivity reactions, thyroid dysfunction, eosinophilia, and arthralgia. The majority of these AEs are mild to moderate in severity and can be monitored and managed in the clinical setting. The goal of engineering a PEGylated form of IL-2 that reduces the treatment-limiting toxicities of aldesleukin, that is, those necessitating in-hospital administration, appears to have been realized with bempegaldesleukin at the doses tested.

Additional details on the clinical experience with bempegaldesleukin are provided in the bempegaldesleukin Investigator's Brochure.

3.3.2 Nivolumab Safety Profile

Extensive details on the safety profile of nivolumab are available in the Investigator's Brochure and will not be repeated herein.

Overall, the safety profile of nivolumab monotherapy as well as in combination with ipilimumab is manageable and generally consistent across completed and ongoing clinical trials with no MTD reached at any dose tested up to 10 mg/kg. Most AEs were low-grade (Grade 1 to 2) with relatively few related high-grade (Grade 3 to 4) AEs. There was no pattern in the incidence, severity, or causality of AEs with respect to nivolumab dose level.

A pattern of immune-related adverse events has been defined, for which management algorithms have been developed; these are provided in [Appendix 6](#). Most high-grade events were manageable

with the use of corticosteroids or hormone replacement therapy (endocrinopathies) as instructed in these algorithms.

Additional details on the safety profile of nivolumab, including results from other clinical studies, are also available in the nivolumab IB.

3.3.3 Bempegaldesleukin and Nivolumab Benefit and Risk Assessment

Bempegaldesleukin has been generally well-tolerated in the clinical studies to date, both as monotherapy as well as in combination with nivolumab, with promising evidence of clinical efficacy and a potentially favorable benefit-risk profile. Bempegaldesleukin has been safely administered in an outpatient setting supported by appropriate clinical monitoring.

Hypotension has been identified as a clinically significant adverse effect of bempegaldesleukin, and can be effectively mitigated by prophylaxis and hydration guidelines. Other risks associated with bempegaldesleukin include IL-2 mediated AEs (eg, flu-like symptoms, rash, pruritus, fatigue, hepatic transaminase elevations, and serum creatinine elevation), infusion related reactions, thyroid dysfunction, eosinophilia, and arthralgia; these AEs are generally mild or moderate in severity, and can be monitored and managed in clinical setting. Cases of thyroid dysfunction (hypothyroidism, hyperthyroidism, thyroiditis), dermatitis, pneumonitis, hepatitis, myocarditis, myositis/myasthenia gravis, and vitiligo/hypopigmentation consistent with immune-mediated mechanism have been observed in patients receiving bempegaldesleukin plus nivolumab, and some of these cases shared clinical characteristics consistent with immune-mediated AEs associated with checkpoint inhibitors.

The continued development of bempegaldesleukin in combination with nivolumab for the treatment of various cancers is warranted based on a positive benefit-risk profile. In addition, the early efficacy data along with the correlative biomarker showing conversion of PD-L1 negative patients to PD-L1 positive patients suggests that the addition of bempegaldesleukin to a checkpoint inhibitor (nivolumab) may change the tumor microenvironment in PD-L1 negative patients such that the combination may contribute to anti-tumor activity with an acceptable safety profile.

In conclusion, the currently available safety data demonstrates that bempegaldesleukin and nivolumab is a well-tolerated immuno-oncology combination therapy. Given the encouraging clinical activity and manageable and generally non-overlapping toxicity profile, the potential for direct benefit in patients warrants continued evaluation of the combination bempegaldesleukin and nivolumab in the clinical setting and supports further development of combination of bempegaldesleukin and nivolumab regimens in patients with cancer. If a participant had severe acute respiratory syndrome coronavirus 2 (SARS-CoV-2) infection during the trial, then the benefit and risk considerations remain the responsibility of the Investigator.

The final ORR and PFS analyses, and the first OS interim analysis (combined with the second OS interim analysis) have been completed using the locked database with a database lock date of 01-Feb-2022. The addition of bempegaldesleukin to nivolumab did not result in a statistically significant improvement in PFS (HR 1.09, 97% CI, 0.88-1.35) or ORR compared to nivolumab monotherapy, and the significance threshold for OS was also not crossed at the combined first and second OS analyses. Given there was no additional clinical benefit in the doublet therapy arm

compared to the monotherapy arm for the primary endpoints of PFS and ORR, the Sponsor, in consultation with the DMC, decided to unblind the trial and to perform no additional formal analyses for the OS endpoint.

After the Sponsor reviewed the topline results from the ORR and PFS final analysis, additional toxicities with no added efficacy were observed in the experimental arm. Therefore participants are required to discontinue bempegaldesleukin and may continue nivolumab monotherapy for the remainder of the study treatment period.

4 OBJECTIVES AND ENDPOINTS

Table 4-1 presents the objectives and endpoints of the study. The final ORR and PFS analyses, and the first OS interim analysis (combined with the second OS interim analysis) have been completed using the locked database with database lock date of 01-Feb-2022. Given there was no additional clinical benefit in the doublet therapy arm compared to the monotherapy arm for the primary endpoints of PFS and ORR, the Sponsor, in consultation with the DMC, has decided to unblind the trial. No additional OS formal analyses will be performed. Any further efficacy analyses, if conducted, will be descriptive.

Per Protocol Amendment 03, the secondary and exploratory objectives except biomarker parameters are no longer applicable. Biomarker sample collection will not be applicable per Protocol Amendment 03. However, exploratory analysis of biomarkers on previously collected samples as per [Section 9.8](#) may be conducted.

Table 4-1: Objectives and Endpoints

Objectives	Endpoints
Primary	

 To compare ORR using RECIST 1.1 for bempegaldesleukin combined with nivolumab and that of nivolumab monotherapy in participants with previously untreated unresectable or metastatic melanoma 	
 ORR by BICR

 To compare PFS using RECIST 1.1 of bempegaldesleukin combined with nivolumab and that of nivolumab monotherapy in participants with previously untreated unresectable or metastatic melanoma 	
 PFS by BICR

 To compare OS of bempegaldesleukin combined with nivolumab and that of nivolumab monotherapy in participants with previously untreated unresectable or metastatic melanoma 	
 OS
Secondary	

 To evaluate efficacy of bempegaldesleukin combined with nivolumab and that of nivolumab monotherapy 	
 CBR, DoR, TTR by BICR per RECIST 1.1 ORR, PFS, CBR, DoR, TTR by Investigator per RECIST 1.1

 To evaluate the association between PD-L1 tumor expression on tumor cells ($\geq 1\%$ or 	
 PFS and ORR by BICR and OS in biomarker population

Table 4-1: Objectives and Endpoints

Objectives	Endpoints
< 1%/indeterminate) and efficacy measures including PFS and ORR by BICR and OS.	

 To evaluate the safety and tolerability of bempegaldesleukin combined with nivolumab and that of nivolumab monotherapy 	
 Safety and tolerability
Exploratory	

 To characterize the effect of nivolumab when administered as monotherapy and in combination with bempegaldesleukin on immune cell populations and markers of immune activation. Tumor tissue may also be explored for potential biomarkers of immune activation. 	
 Biomarker parameters

 To assess efficacy of bempegaldesleukin combined with nivolumab and nivolumab monotherapy based on tumor mutation burden and blood-based tumor mutation burden. 	
 PFS, OS, ORR in Biomarker Population.

 To evaluate PFS after the next line of treatment (PFS2) of bempegaldesleukin combined with nivolumab and that of nivolumab monotherapy in participants with 	
 PFS2 by Investigator per RECIST 1.1

Table 4-1: Objectives and Endpoints

Objectives	Endpoints
previously untreated unresectable or metastatic melanoma	

5 STUDY DESIGN

5.1 Overall Design

This is a multicenter, randomized, open-label, Phase 3 study that will evaluate the efficacy and safety of bempegaldesleukin in combination with nivolumab compared with nivolumab monotherapy in adult and adolescent (≥ 12 years of age) participants with previously untreated unresectable or metastatic melanoma. The study is divided into a Screening period, a Treatment period, and a Long-Term Follow-up period.

Participants will be randomized (1:1) to 1 of 2 treatment arms:

The original treatments in Arm A and Arm B are not applicable per Protocol Amendment 03.

[figure not shown]
- **Arm A:** Bempegaldesleukin 0.006 mg/kg IV Q3W + nivolumab 360 mg IV Q3W (sequential dosing)
- **Arm B:** Nivolumab 360 mg IV Q3W
- Note:
- Bempegaldesleukin dose is based on IL-2 equivalent component.
- Nivolumab dosing in both arms for participants < 40 kg will be weight-based 4.5 mg/kg IV Q3W.

Randomization will be stratified by:

- PD-L1 tumor expression status ($\geq 1\%$ vs $< 1\%$ or indeterminate) based on the PD-L1 IHC 28-8 pharmDx assay)
- BRAF mutation status (V600 mutation positive vs wild type) based on local testing.
- AJCC 8th edition M stage [M0 / M1any[0] (Stage III any LDH or Stage IV Normal LDH) vs M1any[1] (Stage IV Elevated LDH)] based on the screening imaging and laboratory test results.

This study schematic is not applicable per Protocol Amendment 03. Figure 5.1-1 provides the study schematic, and Section 2 outlines the study procedures in the Schedule of Activities.

Figure 5.1-1: Study Schematic

Per Protocol Amendment 03:

- Participants who have completed therapy and are currently in survival follow-up should discontinue from the study immediately if AE reporting requirements have been fulfilled as per Section 9.2.3. Documentation of last overall survival should occur upon discontinuation.
- Participants who have completed therapy and are currently within the 100 days safety follow-up should discontinue from the study once they complete the safety follow up 100 days after the last dose of study treatment if AE reporting requirements have been fulfilled as per Section 9.2.3. Documentation of last overall survival should occur upon discontinuation.
- Participants in Arm A are required to discontinue bempegaldesleukin and may continue nivolumab monotherapy. Participants receiving treatment in Arm A and Arm B will receive nivolumab monotherapy on study at 480 mg IV Q4W. Participants < 40 kg will be administered a body weight adjusted nivolumab dose of 6 mg/kg IV Q4W.
- All participants will have 100 days safety follow-up or until AE reporting requirements have been fulfilled as per Section 9.2.3. Documentation of last overall survival should occur upon discontinuation. The Sponsor will close the study once the last participant has completed the safety follow-up.

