5.1.2 Treatment Period

The treatment period of the study is divided into multiple treatment cycles with associated evaluations and procedures. One cycle of treatment is defined as 3 weeks. Results of the assessments must be reviewed and documented before administering the first dose of the next cycle. Every effort should be made to schedule visits within the protocol-specified windows. Assessments and frequency are described in [Section 2](#).

Participants will be treated until disease progression, death, unacceptable toxicity, symptomatic deterioration, the Investigator's decision to discontinue treatment, the participant's decision to discontinue treatment or withdraw consent, the participant is lost to follow-up, BMS and Nektar Therapeutics decide to terminate the study, or for a maximum of 24 months of treatment. In certain circumstances, participants with progressive disease per RECIST 1.1, but with otherwise stable or improved performance and clinical status, may continue to be treated in the event of a perceived benefit per Investigator; see [Section 8.1.3](#) for treatment beyond progression criteria.

Per Protocol Amendment 03, participants who are currently receiving bempegaldesleukin plus nivolumab are required to discontinue bempegaldesleukin and may continue nivolumab monotherapy. Participants in Arm A and Arm B will receive nivolumab monotherapy at 480 mg IV Q4W. Participants < 40 kg will be administered a body weight adjusted nivolumab dose of 6 mg/kg IV Q4W.

Investigators have the following options for participants who are still on treatment:

- 1) Discontinue bempegaldesleukin and continue nivolumab monotherapy if the participant is assigned to the experimental arm (bempegaldesleukin plus nivolumab) for the protocol-specified duration
- 2) Continue assigned nivolumab monotherapy (i.e. nivolumab) for the protocol-specified duration
- 3) Discontinue the participant from assigned study treatment
- 4) Investigators should inform participants who are still on treatment and those on follow up about the study results and counsel them on treatment choices. Decisions regarding treatment options should be made jointly by Investigators and participants based on a risk/benefit analysis assessed individually for each participant. The counseling and decision should be clearly documented in the medical record of participant. All participants must be re-consented.

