8.2 Discontinuation from the Study

Participants who request to discontinue study treatment will remain in the study and must continue to be followed up to 100 days for protocol specified follow-up procedures with documentation of last overall survival. The only exception to this is when a participant specifically withdraws consent for any further contact with him/her or persons previously authorized by participant to provide this information.

- Participants should notify the Investigator of the decision to withdraw consent from future follow-up **in writing**, whenever possible.
- The withdrawal of consent should be explained in detail in the medical records by the Investigator, as to whether the withdrawal is from further treatment with study treatment only or also from study procedures and/or post treatment study follow-up, and entered on the appropriate CRF page.
- In the event that vital status (whether the participant is alive or dead) is being measured, publicly available information should be used to determine vital status only as appropriately directed in accordance with local law.
- If the participant withdraws consent for disclosure of future information, the Sponsor may retain and continue to use any data collected before such a withdrawal of consent.

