	
be estimated. In addition, to account for potential non-proportional hazard for PFS, sensitivity analyses will be conducted to compare PFS per BICR between treatment groups using weighted log-rank test. Technical details will be given in the SAP.
 
Participants who do not progress or die will be censored on the date of their last evaluable tumor assessment. Participants who do not have any on-study tumor assessments and do not die will be censored on their date of randomization. Participants who started a new anticancer treatment regimen prior to disease progression will be censored on the date of their last evaluable tumor assessment prior to receiving the new antineoplastic regimen. Participants who are lost to follow up will be censored on the date of their last evaluable tumor assessment.

Primary Overall Survival
	
Overall survival (OS) is defined as the time between the date of randomization and the date of death due to any cause. Participants who do not have a date of death will be censored on the last date for which a participant was known to be alive. OS will be analyzed using the stratified log rank test, Cox proportional hazards model, and Kaplan Meier method, similar to PFS. The OS rates at 12 and 24 months will also be estimated. In addition, similar sensitivity analyses to account for potential non-proportional hazard for OS will also be conducted.

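### Minor, conditional: a descriptive OS update using post-Amendment 03 data needs one common censoring date, because survival observation now depends on treatment status

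*Combined protocol and SAP*

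**What the plan says.** Section 5.1 of the protocol sets three exit rules under Amendment 03:

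- Off-treatment participants "currently in survival follow-up should discontinue from the study immediately if AE reporting requirements have been fulfilled".
- Those within 100 days of the last dose leave at day 100.
- Those still on nivolumab may continue and are then covered by the general rule: "All participants will have 100 days safety follow-up or until AE reporting requirements have been fulfilled".

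At each exit, "Documentation of last overall survival should occur upon discontinuation". Section 8.2 adds that participants who ask to stop treatment "must continue to be followed up to 100 days for protocol specified follow-up procedures with documentation of last overall survival". The three-monthly survival contact is marked not applicable in Section 5.1.3 and in Table 2-3, footnote b.

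On treatment duration, Section 5.1.2 says: "Participants will be treated until disease progression, death, unacceptable toxicity, symptomatic deterioration", among other reasons, with a 24-month maximum. Its options at the amendment include "Discontinue the participant from assigned study treatment".

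The OS method in Section 10.3.1 was not adapted. Participants without a date of death "will be censored on the last date for which a participant was known to be alive", and "The OS rates at 12 and 24 months will also be estimated". Sections 4, 10 and 10.3.4 end formal OS testing but leave descriptive efficacy analyses open. The only clinical data cut-off date that the protocol defines, in Section 10.2, serves the ORR population.

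**The concern.** After the amendment, deaths are routinely captured only on treatment or within 100 days of the last dose. Treatment ends mainly for progression, toxicity or deterioration, so those who stay under observation are mostly those who have not progressed. Kaplan-Meier estimation assumes that people censored at a given time have the same future mortality as those still followed. Here the people censored at the amendment are the ones at higher risk.

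An ordinary later data cut-off does not cure this, because the leavers are already censored at their exit. What is at stake is narrow: the within-arm 24-month OS rate in an optional, descriptive update.

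**Working it through.** **1. The plan's own figures reproduce.** OS events = 4(z₀.₉₉₀₅ + z₀.₉₀)² / (ln 0.7)² = 4(2.3455 + 1.2816)² / 0.1272 = 414 (Freedman's formula: 423), against the stated 419. The same formula at alpha 0.03 gives the stated 375 PFS events. The PFS rates in Section 10.1.2 give the stated median of 6.96 months, and 37.6/0.7 = 53.7 months.

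**2. Does the 24-month estimate use post-amendment time?** Section 10.1.1 projects 480 randomized by month 29.9 and 764 by month 38.8. With uniform accrual, an amendment at month 44.2 leaves 764 − 480 × 20.2/29.9 = 440 participants randomized less than 24 months earlier. At month 51.4 the number is 764 − 480 × 27.4/29.9 = 324. So yes.

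**3. Direction.** With equal mortality on and off treatment there is no bias (simulated 64.2% against a true 64.2%). The design figures make equality implausible. The OS hazard is ln 2/37.6 = 0.0184 per month and the PFS hazard from month 9 to 18 is ln(0.46/0.37)/9 = 0.0242. Equal mortality would make 0.0184/0.0242 = 76% of those PFS events deaths without progression.

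**4. Size.** Illness-death simulation, 400,000 subjects per scenario.

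- From the documents: PFS 63/52/46/37% at 3/6/9/18 months (Section 10.1.2) and 32% at 36 months (Section 5.4.1); median OS 37.6 months (Section 10.1.3), used to calibrate survival after progression; the accrual above; the 24-month cap; the 100-day window; 107 days from the lock (01-Feb-2022) to the amendment (19-May-2022).
- Timing: OS interims 1 and 2 were merged, which Section 10.1.3 ties to at least 230 deaths. The model reaches 230 at month 40.7 to 42.9. Adding an assumed 0, 2 or 5 months from cut-off to lock, plus 107 days, puts the amendment at month 44.2 to 51.4.
- Other assumptions: 5/10/20% of PFS events fatal; toxicity stops 10/25% per year; 0/25/50% treated beyond progression for a mean of 4 months; exits immediate or spread over 3 months. That makes 108 scenarios, each with 0, 50 or 100% of on-treatment participants stopping at the amendment.
- Observation ends at max(amendment exit, last dose + 100 days).

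The central case uses 10% fatal, 15% per year toxicity stops, 25% treated beyond progression, a 2-month gap, a 3-month spread and 382 per arm. True 24-month OS is 62.7%.

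| Stop at amendment | Bias over 108 scenarios, points (mean) | Central bias | 95% CI coverage | RMSE: plan's rule / amendment date |
|---|---|---|---|---|
| None | 0.9 to 3.5 (2.1) | 2.0 | 89.5% | 3.2 / 2.8 |
| Half | 0.7 to 2.5 (1.5) | 1.4 | 92% | not computed |
| All | 0.5 to 1.2 (0.8) | 0.9 | 94% | 2.8 / 2.9 |

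With none stopping, a run by timing gave 3.1, 2.3, 1.1 and 0.6 points for an amendment at month 44.2, 47, 51.4 and 54; with all stopping it gave 0.3 to 0.6.

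A second model was calibrated to 0.5^(24/37.6) = 64.2% at 24 months, with the amendment at month 43.3 and nobody stopping. It gave 67.6% (+3.3 points; +1.5 to +4.9 across mortality and toxicity assumptions). The bias vanished for an amendment 24 months after the last randomization.

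**5. Remedies.** One common date at the amendment left a bias within 0.1 point. A plain cut-off 6 or 12 months later left about 1.1 or 2.0 points in the central case. A full survival sweep to 6 months after the amendment gave the lowest RMSE, 2.6. The cut-off used for the lock gave 3.1.

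**The case against.** No post-lock OS analysis is scheduled. Harm needs the sponsor to run an optional analysis, pool post-amendment data, apply no suitable cut-off and report the 24-month rate. Section 10 leaves detailed methods to a separate SAP, which was not supplied and may already set a date. All of this stands and limits the point to a minor, conditional one.

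The exit rule is not absolute. Section 5.1 makes it conditional on completed AE reporting, and Sections 5.1.3 and 9.2.3 keep some off-treatment participants under follow-up. If 30% of them stayed a mean of 6 months (an assumption; the documents give no figure), the bias falls from 2.3 to 2.0 points with none stopping, 1.7 to 1.3 with half and 0.9 to 0.5 with all. This also stands.

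The size is uncertain. Accrual is a February 2021 projection, the stopping share is unknown, and 230 deaths is a floor, so the amendment may have come later than modelled. If everyone stops, the fix brings no gain in accuracy.

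A reader might infer more than the documents support:

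- *That the completed OS interim is biased.* It rests on the 01-Feb-2022 lock, before the exit rules existed.
- *That the treatment comparison is distorted.* With no true difference, the simulated hazard ratio was 1.00 to 1.03 when both arms stopped at the same rate, and at most 1.06 if all of Arm A and none of Arm B stopped.
- *That the confidence interval is too narrow.* In the central case the mean standard error was 2.57 against an empirical SD of 2.56. The interval is off-centre, not too short.
- *That survival data at the amendment are lost.* Status is documented at exit.

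**Conclusion.** The point holds as a minor, conditional one. If a descriptive OS analysis is run on post-amendment data under the last-known-alive rule, the within-arm 24-month rate is biased upward by roughly 0.3 to 3.5 points, about 2 in a central case and up to 5 in the second model. The bias shrinks towards 0.5 point or less if the amendment came late relative to the last randomization or if most on-treatment participants stopped; AE-related retention lowers it a little further.

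The direction rests on mortality being higher off treatment than on, which the design curves make likely but the documents do not state. The size rests on assumed timing, stopping share and event mix. The 12-month rate moves by about half a point or less over the 108 scenarios. The lock analyses and all formal tests are not affected, and the hazard ratio hardly moves.

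**What to change.** In Section 10.3.1, state that any descriptive OS analysis after the lock censors all randomized participants at one common calendar date no later than the first Amendment 03 discontinuations, with deaths after that date not counted. Allow later data only if survival status is obtained to a common later date for all randomized participants. If the SAP already sets such a date, a cross-reference is enough.

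The amendment date is preferable to the lock's data cut-off because it loses less precision. The standard error of 24-month OS per arm rises from about 2.6 to 2.9 points (3.2 at the lock cut-off), and about 1 to 14 later deaths across both arms go unused. There is no net accuracy gain if all on-treatment participants stop at the amendment. A full survival sweep keeps the standard error at 2.6 but means contacting people who have left.

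Separately, as an editorial matter, reconcile Section 8.1.4 with Section 5.1.3 and Table 2-3, footnote b. Its paragraph letting the sponsor request survival data carries no not-applicable label, while the parallel text in the other two places does. It looks like a labelling remnant, but it bears on whether a sweep is permitted.
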